Secondary performance outcomes include the feasibility of inducing, maintaining, and rewarming patients from targeted temperature management using the Esophageal Cooling Device. Specifically, cooling rate, rewarming rate, and the percent of time during the goal-temperature maintenance period within 1°C of goal temperature (typically 33°C, but with some centers using anywhere from 32°C to 36°C) will be measured.

Secondary safety outcomes include evaluation of adverse events including the following: cardiac arrhythmias, severe bradycardia, myocardial infarction/re-infarction, dysphagia, odynophagia, aspiration pneumonia, non-aspiration pneumonia, reflux, esophageal injury, and esophagitis.

Specific definitions of adverse events and the methods used to identify and diagnose each during the treatment and 30-day follow-up phases are as follows:

- Cardiac arrhythmias - recording of atrial or ventricular arrhythmias during course of treatment.
- Severe bradycardia - heart rate < 30/min and necessitating pacing and cessation of TH.
- Myocardial infarction - universal definition of myocardial infarction as per the joint ESC/ACCF/AHA/WHF Task Force for the Redefinition of Myocardial Infarction.[50]
- Dysphagia - report from patient of difficulty in swallowing for more than 24 hours after cessation of device use, diagnosed with a Modified Barium Swallow Study, Videofluoroscopic Swallow Study, or patient self-report.
- Odynophagia - report from patient of pain with swallowing for more than 24 hours after cessation of device use, diagnosed by subjective patient sensation.
- Aspiration pneumonia - demonstration by chest X-ray of evidence of aspiration pneumonia, as diagnosed by treating physician, within 24 hours of cessation of device use.

- Non-aspiration pneumonia - demonstration by chest X-ray of evidence of pneumonia within 24 hours of cessation of device use that is diagnosed by the treating physician as non-aspiration pneumonia.
- Reflux - report of symptoms from patient within 3 days of recovery, with diagnosis via esophageal pH monitoring or endoscopy.
- Esophageal injury - evidence of traumatic and/or ischemic esophageal injuries diagnosed by gastroenterologist evaluation via esophagogastroduodenoscopy as warranted or indicated, and describing the absence of necrosis or not according to the Zargar classification used for caustic injuries within 3 days of recovery .

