- Esophagitis - evidence of esophageal inflammation diagnosed by gastroenterologist evaluation via esophagogastroduodenoscopy if warranted or indicated, and as defined by Savary-Miller and staged from 1 to 4 according to the severity of the disease within 3 days of recovery.

A serious adverse event (SAE) is defined as any adverse event that:

- Results in death
- Is life threatening
- Requires hospitalization or prolongation of existing hospitalization
- Results in persistent or significant disability or incapacity
- Is a congenital abnormality or birth defect

Patient population:

Patient population will consist of 15 patients suffering from traumatic brain injury, in whom the treating clinician has determined that targeted temperature management will be initiated.

Duration of patient's participation in the study

The patient's duration of the participation should be considered as follows:

- From signing of consent form by patient's legal representative and until 30 days if the patient has recovered within 30 days from the consent's signature and is able to sign the ICF personally;
- From signing of consent form by patient's legal representative and until the patient's recovery – patient's ability to sign the consent form (either a full or at least sufficiently partial neurologic recovery that allows the patient to awaken, function, understand conversation, ability to sign personally);
- From signing of consent form by patient's legal representative to patient's death

Inclusion criteria:

Adult patients (age 18 years and over)

Exclusion criteria:

- Patients with known esophageal deformity or evidence of esophageal trauma (for example, known esophageal varices, cirrhosis, history of esophagectomy, previous swallowing disorders, achalasia, etc.).
- Patients with known ingestion of acidic or caustic poisons within the prior 24 hours.
- Patients with less than 40 kg of body mass.
- Patients known to be pregnant.
- Terminal disease or “do not resuscitate order” that could lead to early-onset therapeutic withdrawal (<48 hours after collapse).
- Unstable hemodynamic conditions (defined as intractable severe cardiogenic shock or ECLS requiring) that could lead to multi-organ failure and early-onset death (<48 hours after collapse).
- Pre-existing severe conductive disorder requiring pacing.

Informed consent and ethical considerations:

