After the first 24 hours from the admission of the patient to the hospital Simplified Acute Physiology Score (SAPS) III will be measured.

Daily during day 1-7 if ICU stay the following procedures and assessments will be performed and recorded in the CRFs:

- Sequential Organ Failure Assessment (SOFA) scores;
- GCS scores;
- Pupillary and corneal reflex check;
- Highest body temperature;
- Highest dose and type of vasopressor/inotropic medication;
- The need for pacing;
- Intracranial pressure monitor pressures will be recorded (if measured);
- Recording of a need for mechanical circulatory assistance;
- Mechanical ventilation (if necessary);
- Recording of daily net fluid balance;
- Recording of adverse events;

Daily from day 8 to ICU discharge or day 14 the following records will be made:

- Patient comatose (yes or no);
- Mechanical ventilation (yes or no);
- Renal replacement therapy (yes or no);
- Presence of pneumonia (aspiration/non-aspiration) and sepsis (yes or no)

CPC should be assessed and recorded daily with the last recording being either at discharge, or at the 30 day time point.

Daily from day 1 to day 14 “do not attempt resuscitation order” should be recorded in the CRFs.

Based on investigator’s discretion, the following procedures may be performed if a decision is being contemplated for withdrawal of patient care”:

- Results and time of SSEP, if performed (n20 present bilaterally/n20 present unilaterally/n20 absent);
- Results and time of EEG, if performed.

At ICU discharge or 30 days from admission the following procedures will be recorded if performed (only CPC and GCS are mandatory):

- EEG, MRI, CT (if performed)
- CPC and GCS;

- Esophagogastroduodenoscopy (if performed)

Throughout the entire study:

- Concomitant medications;
- Adverse events

Statistical analysis

Sample size for primary outcome is calculated with an assumption of time to initiate cooling being approximately 5 minutes, with standard deviation of 4 minutes for the esophageal cooling device, and 20 minutes, with standard deviation of 15 minutes, for alternative devices. A power of 80%, and alpha of 5%, yields a sample size of 14 patients (with an equivalent size of historical controls). Sample size for secondary outcome is calculated for a non-inferiority test against the

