current standard (cooling blankets or evaporative cooling). For the endpoint of percent of time over the study period within 1°C of goal temperature (33°C), the treatment effect of the active control is large, since non-treatment results in essentially no attainment of goal temperature. An estimate of effect of the active comparator (M_1) is therefore greater than would be acceptable to use as a base for a non-inferiority margin. Consequently, a more restrictive non-inferiority margin (M_2) is then proposed of 15% (i.e., if the standard maintains goal temperature $+\/-1^\circ\text{C}$ for 60% of the time, and the ECD maintains goal temperature $+\/-1^\circ\text{C}$ for 85% of the time, the lower bound of the 95% CI on the difference between percent time at goal temperature between standard and test device is greater than 70%). Setting the type I error rate to 5%, for an alpha of 0.05, and a power of 80%, for a beta of 0.2, yields a sample size estimate of 15 patients in the study (with another at least 15 patients coming from historical controls with available esophagogastroduodenoscopy evaluation).

Data analysis: as recommended by current FDA guidance documents, both per-protocol (as-treated) and intent-to-treat analyses will be performed.[53] Lower 95% confidence limit for difference between groups must exclude the non-inferiority margins for primary end point in both efficacy and safety.

Abbreviation

ACT - Advanced Cooling Therapy

AE – adverse event

BNP - brain natriuretic peptide

ECG - electrocardiogram

GCS – Glasgow Coma Score

CPC - Cerebral Performance Category

CT – computed tomography

ECD - Esophageal Cooling Device

ECLS - Extra-Corporeal Life Support

EEG – electroencephalogram

LBBB - left bundle branch block

MAP – mean airway pressure

MRI - Magnetic Resonance Imaging

Protocol No ACT TBI-01

Version No 2.0 dated on 08-Dec-2014

OTC – over-the-counter

ROSC - Return of Spontaneous Circulation

SAE – Serious Adverse Event

SAPS – Simplified Acute Physiology Score

SOFA – Sequential Organ Failure Assessment

SSEP - Somatosensory evoked potentials

STEMI - ST-elevated myocardial infarction

TH - Therapeutic Hypothermia

References:

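### Historical controls for percent time at goal must have had an endoscopy, while device patients are scoped only if indicated: the condition does nothing for the temperature endpoint and makes any esophageal comparison uninterpretable

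*Combined protocol and SAP*

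**What the plan says.** The Statistical analysis section bases the secondary-outcome sample size on percent of time within 1°C of goal temperature. It asks for 15 study patients, "with another at least 15 patients coming from historical controls with available esophagogastroduodenoscopy evaluation". The primary-outcome sample size, in the same section, asks for an equal number of historical controls and attaches no endoscopy condition.

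For study patients, endoscopy is discretionary. Under Secondary outcomes, esophageal injury is "diagnosed by gastroenterologist evaluation via esophagogastroduodenoscopy as warranted or indicated", graded on a scale "used for caustic injuries within 3 days of recovery". Esophagitis is "diagnosed by gastroenterologist evaluation via esophagogastroduodenoscopy if warranted or indicated", staged "according to the severity of the disease within 3 days of recovery". Under Study assessments and procedures, the procedures at ICU discharge or 30 days "will be recorded if performed (only CPC and GCS are mandatory"), and the list includes "Esophagogastroduodenoscopy (if performed").

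The Abstract and Study design say in general terms that outcomes will be compared with historical controls in a non-inferiority design. The Data analysis paragraph says that the confidence limit "must exclude the non-inferiority margins for primary end point in both efficacy and safety". It names no esophageal event, and no safety margin appears anywhere.

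The documents do not say why or when controls were scoped, or whether ECD esophageal rates are taken over all treated patients or only those scoped.

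**The concern.** The selection rule and the endpoint do not match. A control's endoscopy is irrelevant to how long that patient stayed near goal temperature. Requiring one can only narrow the control group to patients who had some reason to be scoped, and they may differ in severity, length of stay or survival. No direction can be given for the effect on the temperature comparison.

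The condition makes sense only if someone means to compare esophageal findings. Esophageal injury and esophagitis are listed secondary safety outcomes, and they are the harms most specific to a device that sits in the esophagus. If they are set against these controls, one group is scoped in full and the other by indication. A difference, or the lack of one, could then reflect who was scoped and when, and be read as evidence on esophageal safety.

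**Working it through.** **1. Does endoscopy enter the stated 15?** Inputs from the Statistical analysis section: 60% (standard), 85% (ECD), margin 15 points, alpha 5%, power 80%. Sidedness and a standard deviation are not stated, so percent time is treated here as a binary proportion, with equal groups.

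n per group = (z_alpha + z_power)² × [p_C(1−p_C) + p_E(1−p_E)] / (p_E − p_C + margin)²

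- One-sided 5%: (1.645 + 0.842)² × (0.60×0.40 + 0.85×0.15) / (0.25 + 0.15)² = 14.2, rounded up to 15. This matches the plan.
- One-sided 2.5%: (1.960 + 0.842)² × 0.3675 / 0.16 = 18.03, rounded up to 19. This does not match.

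No endoscopy quantity appears in the formula, so removing the condition leaves the stated 15 as it is.

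**2. What could unequal scoping do to esophageal rates?** The documents give no lesion or scoping rates, so everything in this step is assumed for illustration. Let r be the true risk, the same in both groups; s1 the probability that an injured patient is scoped; s0 the probability that an uninjured patient is scoped.

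- Observed rate over all treated patients: r × s1
- Observed rate over scoped patients only: r×s1 / [r×s1 + (1−r)×s0]
- Observed rate if everyone is scoped routinely: r

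Take r = 5%, s1 = 0.8, and s0 = 0.05 or 0.20.

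- Over all treated: 0.05 × 0.8 = 4%.
- Scoped only, s0 = 0.05: 0.04 / (0.04 + 0.0475) = 45.7%.
- Scoped only, s0 = 0.20: 0.04 / (0.04 + 0.19) = 17.4%.

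| Control scoping | ECD denominator | Control rate | ECD rate |
|---|---|---|---|
| Routine | All treated | 5% | 4% |
| For cause | All treated | 17.4% to 45.7% | 4% |
| For cause | Scoped only, same s1 and s0 in both groups | Equal | Equal |
| For cause, s0 = 0.05 | Scoped only, s0 = 0.20 | 45.7% | 17.4% |
| Routine | Scoped only | 5% | 17.4% to 45.7% |

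The first row is 0.75 versus 0.60 expected events in 15 patients, too small to see. The fourth row reverses if the two scoping thresholds are exchanged. Letting s1 run from 0.5 to 1.0 widens the scoped-only range to 11.6% to 51.3%. Timing is not in the formulas: controls scoped late, after lesions had healed, would show a lower rate in any row.

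**3. How much could ECD patients show on their own?** With the same assumptions, the expected number scoped of 15 is 15 × 0.0875 = 1.31 to 15 × 0.23 = 3.45. The chance that none is scoped is (1 − 0.0875)^15 = 25.3% to (1 − 0.23)^15 = 2.0%. The exact two-sided 95% upper limit for no events in n patients is 1 − 0.025^(1/n): 21.8% for 0/15 and 70.8% for 0/3.

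**The case against.** The strongest reply is that the plan never writes down an esophageal comparison. It speaks of comparing outcomes in general and of evaluating adverse events. No esophageal hypothesis, test or margin exists, and the Data analysis sentence speaks of the primary end point, which is time to initiation. This stands: the comparison is implied, and the criticism of it is conditional on its being made. It does not explain why controls for a temperature endpoint must have had an endoscopy.

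A second reply is that the magnitudes come from assumed rates. This also stands. The grid shows that the contrast is indeterminate; it does not estimate a bias.

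A third is that these are secondary, unpowered outcomes in a 15-patient feasibility study. That limits the weight of the point, but the remedy is correspondingly light.

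A reader might infer that the design flatters the device. The documents do not support that: control scoping could have been routine, for cause or late, and the ECD denominator is open, so the contrast can go either way. A reader might equally infer that scoping both groups for cause and counting only scoped patients makes the rates comparable. That holds in expectation only if the scoping probabilities are the same in both groups, and closely monitored prospective patients and historical charts need not share a threshold.

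**Conclusion.** The point holds as an unexplained control-selection condition combined with unequal ascertainment, and it should be fixed. The textual facts are firm: controls for the secondary outcome must have been scoped, ECD patients are scoped only if indicated, and the reason and timing of control scoping and the ECD denominator are not given.

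For percent time at goal, the condition serves no purpose and may make the controls unrepresentative, in an unknown direction. For esophageal injury and esophagitis, any comparison with these controls could show nothing or a large difference in either direction when the true risks are equal. The sizes shown rest wholly on the assumed 5% risk and scoping probabilities.

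Two further inferences are not supported. The primary outcome is not shown to be affected, because its controls carry no endoscopy condition. And although removing the condition leaves the stated 15 unchanged, this does not verify 15, which reproduces only at one-sided 5% with percent time treated as a binary proportion.

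**What to change.** 1. In the secondary-outcome sample-size text, replace the endoscopy condition with wording such as: *at least 15 historical controls with traumatic brain injury, treated with targeted temperature management by cooling blankets or evaporative cooling, meeting the study's eligibility criteria, with temperature records sufficient to calculate percent time within 1°C of goal, and selected by these criteria without reference to temperature results or safety outcomes*. Brain injury and temperature management need naming because the only listed inclusion criterion is adult age.
2. Report ECD esophageal injury and esophagitis descriptively: number scoped, reason, timing, number affected, and exact 95% confidence intervals over scoped and over all treated patients.
3. Make no between-group or non-inferiority claim on these two events unless both groups share one ascertainment rule, time window and denominator. The sponsor should state whether the efficacy-and-safety sentence under Data analysis is meant to cover them, since no safety margin is given.
4. If an endoscopy-selected control series is kept, show it separately with its source, reason for scoping, timing and denominator.

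The cost is protocol wording and some chart-selection work, with no extra endoscopies or study patients. The documents do not show how many eligible charts exist. What is given up is a controlled conclusion on esophageal events, which 15 patients could not support in any case: even 0/15 leaves an upper limit of 21.8%.

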of other existing methods such as invasive methods.[47] The Esophageal Cooling Device (shown in Figure 1 and Figure 2) is a multichambered silicone heat exchanger that is placed in the esophagus to provide highly efficient heat transfer to/from a patient while simultaneously maintaining access to the stomach to allow gastric suctioning, decompression, and drainage, as usually performed in such patients in emergency departments, operating rooms, and intensive care units.

[figure not shown]

Figure 1. Photograph of the Esophageal Cooling Device (ECD).

The esophagus is in close proximity to blood flow from the heart and great vessels, and the Esophageal Cooling Device is designed to take advantage of this heat exchange environment. The Esophageal Cooling Device's ability to decompress the stomach and avoid distention of the esophagus away from the device ensures good contact with the esophageal mucosa, and thus maximizes heat transfer from the patient. The Esophageal Cooling Device replaces the standard orogastric tube which is placed in the target patient population as a routine standard of care, is made of standard medical-grade silicone, and is generally similar in size and shape to the orogastric tubes currently used. Initial mathematical and animal studies have shown strong support for the efficacy and safety of the Esophageal Cooling Device.[47-49]

[figure not shown]

Figure 2. The Esophageal Cooling Device (ECD) shown in place in the esophagus (replacing the routine gastric tube placed in the target population as a standard of care), and located behind the trachea (containing the endotracheal tube which is placed in the trachea routinely to provide ventilation in the target patient population).

Study design:

Prospective, interventional study evaluating the feasibility and safety of the Esophageal Cooling Device in 15 patients suffering from traumatic brain injury and treated with targeted temperature management. Comparison of outcomes will be made to historical controls, and analysis will utilize a non-inferiority design.

Primary outcome:

Time to initiation of targeted temperature management, as measured from the time a decision is made to begin targeted temperature management, to the time the esophageal cooling device is in place.

Secondary outcomes:

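### The only success rule cannot be applied as written: the primary time has no margin in minutes, the one margin (15%) belongs to a secondary outcome, and no primary safety end point or safety margin exists

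*Combined protocol and SAP*

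**What the plan says.** The abstract and Study design declare a non-inferiority analysis against historical controls. The Primary outcome section names one primary: the time from the decision to start temperature management "to the time the esophageal cooling device is in place". Shorter is better. The Secondary outcomes section places percent time within 1°C of goal, and every adverse event, among the secondary outcomes.

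The Statistical analysis section sizes the two efficacy outcomes separately.

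- **Primary.** "Sample size for primary outcome is calculated with an assumption of time to initiate cooling being approximately 5 minutes" (SD 4) for the device and 20 minutes (SD 15) for alternative devices. "A power of 80%, and alpha of 5%, yields a sample size of 14 patients (with an equivalent size of historical controls"). No margin appears.
- **Percent time.** The sentence opening "Sample size for secondary outcome is calculated for a non-inferiority test against the" ties the non-inferiority calculation to this outcome. "Consequently, a more restrictive non-inferiority margin (M_2) is then proposed of 15"%. The worked example takes 60% for standard and 85% for the device, and requires that the lower bound "on the difference between percent time at goal temperature between standard and test device is greater than 70"%. The result is 15 device patients and at least 15 "historical controls with available esophagogastroduodenoscopy evaluation".

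The data-analysis paragraph then gives the success rule: "Lower 95% confidence limit for difference between groups must exclude the non-inferiority margins for primary end point in both efficacy and safety".

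**The concern.** The rule needs a margin for the primary efficacy end point, a primary safety end point and a safety margin. The plan supplies none of these. The 15% margin cannot be carried over to the primary: it is on a different scale (percentage points, not minutes) and runs in the opposite direction (higher is better). The rule also leaves the sign of the difference open. A lower limit suits a time only if the difference is control minus device.

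Two consequences follow. If the device turns out only moderately faster than control, equal to it or slower, pass or fail depends on a number of minutes that is not written down and could be chosen after the data are seen. And the safety half of the rule cannot be applied whatever the results are.

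**Working it through.** **1. What the rule needs and what the plan gives**

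| Rule needs | Plan gives |
|---|---|
| Margin in minutes for the primary | None; sized as a plain difference, 5 vs 20 |
| Direction of the difference | Not stated |
| Primary safety end point | None; all safety outcomes are secondary |
| Safety margin | None |

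**2. The plan's n = 14 for the primary**

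Inputs (Statistical analysis): means 5 and 20, SDs 4 and 15, power 80%, alpha 5% with sidedness not stated.

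- SE = √(4²/14 + 15²/14) = 4.149; Welch df 14.84; t = 2.133; noncentrality 15/4.149 = 3.62.
- Two-sided 5% Welch power, normal theory: 92.1% at 14 per group and 93.9% at 15. Power passes 80% at 11 per group (83.3%; 78.8% at 10).
- With gamma-distributed times of the same means and SDs (simulated), power at 14 per group is 98.6%.
- Of the methods tried, only SD 15 in both groups with a one-sided 5% t-test returns 14 (82.4%; 79.7% at 13). The two-sided t-test on that basis needs 17.

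**3. The plan's n = 15 for percent time**

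Treating 60% and 85% as binomial proportions, with margin 15 points:

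- n = (z_α + 0.842)² × (0.24 + 0.1275) / (0.25 + 0.15)².
- One-sided 5%: 14.2, so 15, which reproduces the plan. One-sided 2.5% (a two-sided 95% limit): 18.03, so 19.
- Power at 15 vs 15: 0.40/√(0.3675/15) = 2.556. Φ(2.556 − 1.645) = 81.9%; Φ(2.556 − 1.960) = 72.4%.
- With 15 device patients and 21 controls, two-sided 95% limit: 0.40/√(0.1275/15 + 0.24/21) = 2.833; Φ(2.833 − 1.960) = 80.9%.

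The binomial basis is the worst case. The SDs it implies, √0.24 = 49 and √0.1275 = 36 points, are the largest that a 0-100% measure with those means can have. The documents give no SD.

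**4. The 70% bound**

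The planned difference is 85 − 60 = 25 points, and a lower limit cannot exceed its own estimate, so a bound above 70 cannot be met at the planned effect. The figure looks like 85 − 15, a level and not a difference. A 15-point margin means a lower limit of device minus standard above −15 points.

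**5. Does the missing margin in minutes matter?**

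Planned effect, 14 per group: −15 ± 2.133 × 4.149 = −23.9 to −6.1 minutes. This passes at any non-negative margin.

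Other effects: 200,000 simulated trials each, 15 vs 15, control 20 minutes (SD 15). A pass is an upper limit of the two-sided 95% Welch CI (device minus control) below the margin. Device values and margins are my assumptions. Ranges cover gamma and normal models.

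| Assumed device | Margin 0 | 5 min | 10 min |
|---|---|---|---|
| 12 min, SD 9 | 39-40% | 79-83% | 97-98% |
| 20 min, SD 15 (equal) | about 2% | 14-15% | 42-45% |
| 25 min, SD 15 | under 1% | 2-3% | 14% |

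With 30 controls, the 12-minute device passes about 58-60% at zero and about 94% at 5 minutes.

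**6. Could a safety margin be met?**

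Exact enumeration, 15 vs 15, two-sided 95% Newcombe interval, same true rate in both groups (rates and margins assumed):

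| True rate | 15-point margin excluded | 20-point margin excluded |
|---|---|---|
| 5% | 26% | 31% |
| 10% | 23% | 33% |
| 20% | 17% | 28% |

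Even 0 vs 0 events leaves an upper limit of 20.4 points.

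**The case against.** This is a 15-patient feasibility study, the planned effect passes under any sensible margin, and the illustrations rest on device times, margins and event rates that the plan does not contain. All of that is true. The illustrations show how far the verdict could move; they do not measure an error. But the sponsor chose a formal confidence-limit rule, and a rule that cannot be applied needs repair at any sample size.

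A reader might infer four stronger things, which the documents do not support.

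- **That the primary is underpowered.** The stated SDs give more than 80%, so 14 is conservative.
- **That the time comparison is impossible** because controls never receive the device. The sample-size text gives a control time of 20 minutes for alternative devices, so a matching event is intended. Only its definition is missing.
- **That percent time needs 19 device patients.** That figure holds for a 1:1 comparison on the worst-case variance. The plan allows more than 15 controls.
- **That a zero margin is what the plan means.** The primary calculation is consistent with one, but no hypothesis is stated and the declared design is non-inferiority.

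The request for controls with endoscopy suggests that an esophageal comparison was in mind. It names no end point or margin, and in device patients endoscopy is done only if indicated.

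**Conclusion.** The point stands and should be fixed. The success rule calls for margins that the plan does not contain, its only margin belongs to a secondary outcome, the safety half has no named end point, and the 70% bound contradicts the example's own 25-point difference. The stated 80% power for the primary also does not follow from its inputs: about 92% under normal theory and about 99% under a gamma model.

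The practical risk is conditional. At the planned 15-minute advantage the time verdict does not depend on the margin. For a device assumed equal to control, the chance of passing rises from about 2% to 42-45% as the margin goes from 0 to 10 minutes. These figures assume 15 vs 15 and a control SD of 15. I am confident of the textual mismatch, which does not depend on any of these assumptions.

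**What to change.** (a) **Primary.** Before any times are compared, either state and justify a margin in minutes and the direction of the difference, which keeps the declared non-inferiority design; or declare a zero-margin comparison (upper limit of the two-sided 95% Welch CI for device minus control below 0) and confine the non-inferiority label to percent time. In both cases, define the control end time as the matching event, comparator cooling device in place, as the historical records can supply it.

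(b) **Power statement.** Give about 92% at 14 per group (SDs 4 and 15, two-sided 5% Welch, normal theory), and note that it is higher if times are skewed as in a gamma model. No patients need be added.

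(c) **Percent time.** Replace the 70% bound with a lower limit of device minus standard above −15 points. State the sidedness and an assumed between-patient SD. If a two-sided 95% limit is meant, about 21 controls restore 80% power on the binomial basis with 15 device patients.

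(d) **Safety.** Remove safety from the formal rule and report each adverse event as a count with an exact 95% CI; or name the end point, its margin and the denominator in each group, noting that a 15- to 20-point margin is unlikely to be excluded at 15 vs 15.

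Cost: amended wording in the abstract, Study design, Primary outcome and Statistical analysis sections, one control definition, and possibly more historical records. A zero margin is harder to meet for a moderately faster device (39-40% against 79-83% at 5 minutes in the 12-minute example at 15 vs 15). Removing safety from the rule gives up a formal safety claim.
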